All persons assisting with the research will have access to the protocol through the CICERO website. Prior to the commencement of the study, the research team members will have an introductory meeting with the PI where they will be educated about the protocol, procedures and duties. In addition, regular study meetings will be organized where the team members will be updated about any changes in duties, functions, and responsibilities. Individualized training of study team members will be completed by the study coordinator as needed. Study team members will also complete all necessary institutional training sessions necessary for compliance with policies and procedures. Study team members involved in the MyHealtheVet Secure Messaging research communication will have additional training through the VAMHCS MyHealtheVet Education center.

ID: VIEW4DF83CB976400
Name: v2_Resources

Sites Where Research Activities Will Be Conducted

1 * Is this study a:

Multi-Site
 Single Site

2 * Are you relying on an external IRB (not UM) to be the IRB of Record for this study?

Yes No

3 * Are any other institutions/organizations relying on UM to be the IRB of Record for this study?

Yes No

3.1

Attach the applicable regulatory documents here (i.e., IRB Authorization Agreement (IAA), FWA, local ethics approval, other IRB approvals, etc.). Final UM approval will be contingent upon final execution of all required regulatory approvals:

Name	Created	Modified Date
------	---------	---------------

There are no items to display

4 * Is UM the Coordinating Center for this study? (Applicable for multi-site studies. A Coordinating Center is responsible for overall data management, monitoring and communication among all sites, and general oversight of conduct of the project.)

Yes No

5 Is VA the Coordinating Center for this study? (Applicable for Collaborative studies between the VA, UM and other sites. A Coordinating Center is responsible for overall data management, monitoring and communication among all sites, and general oversight of conduct of the project)

Yes No

6 * Institution(s) where the research activities will be performed:

University of Maryland, Baltimore
 University of Maryland, Upper Chesapeake Kaufman Cancer Center
 VAMHCS
 UMB School of Medicine
 Marlene and Stewart Greenebaum Cancer Center
 University Physicians Inc.
 Shock Trauma Center
 General Clinical Research Center (GCRC)
 Maryland Psychiatric Research Center (MPRC)
 Johns Hopkins
 International Sites

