After obtaining informed consent, and completing baseline testing, participants will be randomized to one of the above three study arms. Participants and their caregivers will be provided the option at the time of consent to participate in the VA MyHealtheVet Secure Messaging Pilot Study. Those consenting to this option will be enrolled in the pilot upon randomized to the Delayed Entry UC Group or the Home-based Telerehabilitation (HBT+TTT) group. Those randomized to the lab-based training (LBT+TTT) will NOT be enrolled in the pilot.

Overall study randomization will be stratified based on the participant's baseline Fugl-Meyer (FM) score to prevent selection bias and generate intervention groups with similar impairment levels. Low baseline scores will fall into the range of 19-29 out of 66 max, and high scores in the range of 30-50 out of a 66 max. To account for a 15% attrition rate, we will randomize 78 subjects to achieve an effective sample size of 66 (22 per group). Based on our prior study, we anticipate 73% will be in the low FM group, and 27% in the high FM group. This gives us about 57 subjects in the low FM group and the remaining 21 subjects in the high FM group. To reduce the potential imbalance among different intervention groups, we will block randomize separately for subjects in each baseline FM stratum. To randomly allocate about 57 subjects (yielding to an effective sample size of 48) in the low FM stratum and 21 subjects (yielding to an effective sample size of 18) in the high FM stratum to the HBT+TTT (H), LBB+TTT (L) and delayed entry UC groups with equal proportion, the Biostatistician will generate a permuted block randomization schedule with a block size of 6, using a statistical software, SAS (SAS Institute Inc., NC, USA). This randomization schedule will link each subject sequence number in this stratum with an intervention group.

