5 * **Explain how each individual providing consent will be fully informed and kept fully informed regarding the reasonably foreseeable impact of the research on the fetus:**

Pregnancy will be ascertained and documented during the screening process through verbal asking. If a participant becomes pregnant during the course of the study we

will ask her to notify us. At that time it will be the participant's choice to continue or withdraw.

This research should not pose any risk to the fetus or mother, and may have potential benefit on future care if the mother is able to use her arms better for activities of daily living.

6 * Will inducements, monetary or otherwise, be offered to terminate a pregnancy?

Yes No

7 * Will individuals engaged in the research have any part in any decisions as to the timing, method, or procedures used to terminate a pregnancy?

Yes No

8 * Will individuals engaged in the research have any part in determining the viability of a neonate?

Yes No

ID: V1EW4E0E5195C0000

Name: v2_Vulnerable Populations - Pregnant Women / Fetuses

Eligibility

1 * Do you have an existing Eligibility checklist(s) for this study?

Yes No

1.1 If Yes, upload here. If you need a template, you can download it by clicking **HERE**. The checklists you upload will also be available under the Documents tab of this application.

Name	Created	Modified Date
------	---------	---------------

There are no items to display

1.2 If No, create an eligibility checklist below:

List inclusion criteria (List each Inclusion Criteria individually, using the ADD button):

Number Criteria

View 1	Age 18 years or older.
View 2	Have a clinically defined unilateral hemiparetic stroke with radiologic exclusion of other diagnosis.
View 3	Stroke onset of at least 6 months prior to enrollment.
View 4	Present with moderate to severe arm impairment based on a Fugl-Meyer score ranging from 19-50 out of 66.
View 5	No previous experience using the BATRAC.
View 6	Ability to use and interact with the tele-rehabilitation platform according to study protocol.
View 7	Have an identified individual/caregiver to perform the TTT exercises if randomized to the Home Telerehabilitation group.

List exclusion criteria (List each Exclusion Criteria individually, using the ADD button):

Number Criteria

View 1	Musculoskeletal diagnosis or significant arm pain that would interfere with positioning and use of the intervention (BATRAC) devices.

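### The protocol prints one fixed block size of 6 and describes no allocation concealment, so staff who track allocations by stratum could know about 14 of 78 assignments in advance

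*Combined protocol and SAP*

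**What the plan says.** Under Justification, Objective, & Research Design, item 2, the Biostatistician is to produce a "permuted block randomization schedule with a block size of 6" in SAS. The arms are equal: participants are allocated "in the high FM stratum to the HBT+TTT (H), LBB+TTT (L) and delayed entry UC groups with equal proportion", and the same holds in the low stratum. Blocking is by stratum: "we will block randomize separately for subjects in each baseline FM stratum". The planned numbers follow: "we will randomize 78 subjects to achieve an effective sample size of 66 (22 per group"), and "This gives us about 57 subjects in the low FM group and the remaining 21 subjects in the high FM group". The schedule ties each sequence number in a stratum to a group. Randomisation comes after consent and baseline testing. The stated purpose of stratifying includes preventing selection bias.

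The Resources page, item 4, says: "All persons assisting with the research will have access to the protocol through the CICERO website". Participant Selection, item 2, gives the same enrolment (98) locally and worldwide, so there is one site. The design is labelled single blind, and only the evaluator of outcomes is described as blinded. Informed Consent Process, item 4, lets the principal investigator or any trained team member take consent. Inclusion criterion 6 is a matter of judgement: "Ability to use and interact with the tele-rehabilitation platform according to study protocol".

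No section says who keeps the schedule, how an assignment is released, or that upcoming assignments are hidden from those who screen and enrol.

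**The concern.** Therapists and coordinators see each allocation through lab visits, home set-up or weekly calls. The stratum follows from the baseline Fugl-Meyer score (19–29 or 30–50). Add a constant block size that staff can look up, and the end of every block can be worked out. At one site randomising 78 people over three years, a running tally is easy to keep.

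Foreknowledge matters because it lets someone influence who enters next, by timing a visit or by how a judgement-based criterion is applied. Stratifying on Fugl-Meyer balances impairment; it does not conceal the next assignment, and concealment is what guards against selection bias. A blinded evaluator does not repair selection at entry, and neither does intention-to-treat. The primary test is an unadjusted two-sample t test with 22 evaluable per arm, so any imbalance created at entry would pass straight into the estimate. The regression planned as an alternative can adjust only for covariates that were measured.

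**Working it through.** **Inputs.** All come from Justification, Objective, & Research Design, item 2: block size 6; three equal arms, hence 2 per arm per block; two strata of about 57 and 21; 78 randomised; 66 evaluable; 15% attrition.

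**The plan's own figures.** 66 / (1 − 0.15) = 77.6, rounded up to 78. 0.73 × 78 = 56.9 and 0.27 × 78 = 21.1. The numbers 78, 57 and 21 are reproduced. The documents give no figure for predictability.

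**Within one complete block.** The results below come from enumerating the 90 distinct orderings of AABBCC. The observer knows the block size and all earlier allocations in that stratum.

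| Place in block | Known with certainty | At least one arm ruled out | Best guess correct |
|---|---|---|---|
| 1 | 0 | 0 | 0.333 |
| 2 | 0 | 0 | 0.400 |
| 3 | 0 | 0.2 | 0.500 |
| 4 | 0 | 0.6 | 0.533 |
| 5 | 0.2 | 1 | 0.600 |
| 6 | 1 | 1 | 1.000 |
| Sum | 1.2 | 2.8 | 3.367 |
| Sum / 6 | 20.0% | 46.7% | 56.1% |

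Place 5 is certain only when the last two places belong to the same arm, which has probability 1/5. At place 4 no arm is exhausted only if the first three allocations all differ: 1 × 4/5 × 2/4 = 0.4, leaving 0.6.

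**Over the planned 78.** 57 = 9 × 6 + 3 and 21 = 3 × 6 + 3. That is 12 complete blocks, plus 3 leftover participants in each stratum who occupy places 1 to 3.

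- Certain: 12 × 1.2 = 14.4, and 14.4 / 78 = 18.5% (low stratum 10.8 / 57 = 18.9%; high stratum 3.6 / 21 = 17.1%).
- An arm ruled out: 12 × 2.8 + 2 × 0.2 = 34.0, and 34.0 / 78 = 43.6%.
- Best guess correct: 12 × 3.367 + 2 × (0.333 + 0.400 + 0.500) = 42.9, and 42.9 / 78 = 55.0%, against 33.3% by chance.

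**With mixed block sizes.** This part is simulated for 57 + 21 participants. It assumes the sizes are drawn with equal probability, and that the observer knows the possible sizes but not their order.

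| Sizes | Certain | Arm ruled out | Best guess correct |
|---|---|---|---|
| 6 only | 18.5% | 44% | 55% |
| 6 and 9 | about 4.9% | about 13.5% | about 54% |
| 3, 6 and 9 | about 3.5% | about 10% | about 55% |

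Of 78 allocations, 4.9% is about 3.8 and 3.5% is about 2.7. A mix of 3 and 6 is a weaker choice: about 8.5% stay certain, and the best guess is right about 57% of the time.

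**The case against.** The strongest reply is that the figures describe what a determined observer could know, not what anyone does. That person must know the block size, keep a list by stratum, know the next candidate's stratum and control entry. The Fugl-Meyer test is done by an evaluator blinded to allocation, so the stratum is not established at the first telephone or records screen. Randomisation also waits for consent and baseline testing. Steering would therefore have to happen late, and delayed-entry participants later receive active training, which weakens the motive. All of this stands. It narrows the opportunity, but late withholding or timing of entry remains possible.

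A second reply is that mixed blocks leave the best-guess rate where it was, and steering does not need certainty. That also stands, and it is why concealed release belongs in the remedy alongside the block sizes.

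A third is that the change may come late. The file lists safety-board minutes from 2017, consent forms dated 2019 and returning participants, so enrolment may be under way. Staff cannot unlearn the number 6, but new sizes for the remaining schedule make it much less useful to them.

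Three stronger readings are tempting. A reader might infer that allocation has been manipulated or the result biased; nothing in the documents shows this, and no effect on Wolf Motor Function Test change can be estimated from them. A reader might call the trial open-label with staff instructed to study the block size; the documents say single blind with a blinded evaluator, and that staff have access to the protocol and are educated about it. A reader might apply the 20% rate to everyone and get 0.20 × 78 = 15.6; that ignores the six leftover participants, whose assignments are never certain.

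**Conclusion.** The weakness is real and cheap to prevent. As written, about 14 of 78 planned allocations (18.5%) could be known for certain in advance, at least one arm could be ruled out for about 44%, and a best guess would succeed about 55% of the time. These sizes assume strata of 57 and 21, allocations filled in sequence, and an observer with a complete list for each stratum. They measure guessability, not bias. The later randomisation of delayed-entry participants to an active arm is not included, because no method is given for it. The lack of a described concealment step is a gap in the text; it does not prove that none is used in practice.

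**What to change.** For the schedule, or for whatever remains of it if enrolment has begun:

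1. Use randomly mixed block sizes within each Fugl-Meyer stratum, for example 6 and 9, or 3, 6 and 9.
2. Remove the block sizes from the shared protocol and keep them in the Biostatistician's restricted file.
3. State who holds the schedule, and have each assignment released one at a time from that file by someone not involved in screening or enrolment. Keep the existing rule that this follows consent and baseline testing.

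The cost is a few lines of SAS code, a short paragraph of protocol text and a named person to release assignments. Sample size and planned analyses do not change. The statistical price is slightly larger possible arm imbalance: the greatest difference between two arms within a stratum at any point rises from 2 (blocks of 6) to 3 (blocks of 9). This matters mainly in the high stratum, where 21 / 3 = 7 per arm are expected.

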The VA Maryland Health Care System (VAMHCS) desires to test secure messaging in My HealtheVet (MHV) for communication with research participants in the IRB approved (HP-60526), VA Funded Stroke Rehabilitation Trial "Translating Intensive Arm Rehabilitation in Stroke to a Telerehabilitation Format" aka TeleBATRAC. We are working collaboratively with the Veterans and Consumers Health Informatics Office, VHA Office of Analytics, VA Office of Connected Care, and the Office of Research and Development. We aim to assess potential and specific concerns articulated by our national collaborations, which have included: Secure Messaging triage team naming conventions, procedures for the registration, authentication and secure messaging Opt-In for veteran and non-veteran research participants, association with the study triage team, training of study participants and research triage team recipients, informed consent (to include visibility of secure messaging research communication and data to clinical management teams), management of messages and retention of data, ease of message reassignment, the identification of unintended consequences, and development and collection of data and information to inform future VA research policy and guidance.

MyHealtheVet Secure Messaging Pilot Aims and Hypotheses

Aim 1: To develop and pilot test a Home-based stroke rehabilitation program using the MHV patient portal and secure messaging as the communication delivery system.

Aim 2: To assess for differences in eHealth literacy and self-efficacy between the Delayed Entry Usual Care and the Home-based rehabilitation group using MHV secure messaging.

Hypothesis 1: Home-based MHV stroke survivor & caregivers' intervention group Web-Based Learning Self-Efficacy Scores will meet or exceed the Delayed Entry Usual Care group.

Hypothesis 2: Home-based MHV stroke survivors and caregivers' intervention group eHEALS Health Literacy Scale will meet or exceed the Delayed Entry Usual Care group scores.

Aim 3: Determine efficacy of the two (2) one-hour structured MHV training on stroke survivors and caregivers Web-Based Learning Self-Efficacy Scores (WBLSES) and eHEALS scales.

Hypothesis 1: Home-based MHV stroke survivors and caregivers' intervention group WBLSES will exceed the baseline scores at the end of the clinical trial demonstrating improved comfort and skill in using the MHV patient portal.

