Each patient will be enrolled in the study for 18 training sessions (spread over a maximum of 9 weeks to allow for missed visits due to transportation/weather or minor illness) to complete the intervention as described below. Participants will be asked to return for a retention follow-up after 8 weeks of no training for a maximal study commitment of 17 weeks for those immediately randomized and 23 weeks for those enrolled in the delayed entry group. All repeated outcome measures will be conducted at the VA Annex by a study evaluator blinded to the intervention assignment and will occur at baseline, training completion, and at the 8 week retention follow-up. Additionally, all participants in the Home-based BATRAC telerehabilitation group will be provided with a VA's MyHealtheVet website account (www.myhealth.va.gov) to access the already established educational features and resources about stroke, exercise and caregiver support. Every effort will be made for MyHealtheVet Secure Messaging Pilot study participant appointments to be coordinated with the Primary Study appointments to avoid undue travel.

Intervention and Training

1) Home-based BATRAC telerehabilitation: The BATRAC training platform will be used in conjunction with the VA MyHealtheVet website. This group will have an upgraded MyHealtheVet account to access the Secure Messaging Option for VA approved electronic messaging to the study therapist. Training in use will take place at the Baltimore VA MyHealtheVet Educational Office (2nd floor). MyHealtheVet allows for asynchronous communication with the study therapist, and will store performance information entered by the participant and caregiver related to arm exercise duration, repetitions completed and distances reached. This account can be securely linked and is VA approved for use on any home device (computer, cell phone or tablet) with internet. A MyHealtheVet training visit at the VA and a home visit to verify access, and use with be completed with participants in this group as well as their identified caregivers.

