Participants and caregivers consenting to the option of videoconferencing with the study team via the VA's "VA Video Connect" app, in addition to the VA's MyHealtheVet website described above, will be trained for approximately 5 to 10 minutes on how to use this app when they receive training on how to use the MyHealtheVet website. The "VA Video Connect" app uses encryption to ensure a secure and private session, and it allows quick and easy health care access from any mobile or web-based device; more information on this app is at <https://mobile.va.gov/app/va-video-connect>. Adding the option for videoconferencing communications via the VA's "VA Video Connect" app would allow for an additional means of communication for participants randomized to the home-based telerehabilitation group--besides just phone calls and asynchronous private messages sent back and forth on the MyHealtheVet website. Videoconferencing communications also would allow for these participants and study team members to, in real time, ensure that participants are completing rehabilitation interventions at home properly.

Participants and caregivers consenting to the option of taking part in the VA MyHealtheVet Secure Messaging Pilot study will be seen for baseline Standard Evaluations (eHeals, Web-based Self-Efficacy & MoCA, Post-training Interviews) following randomization and prior to initiation of the study intervention. Those randomized to the Home-based telerehabilitation will receiving training in the appropriate use of MHV secure messaging for research communication and will be interviewed immediately after training to ensure that they feel confident in their ability to use the MHV portal and secure messaging to communicate with the research team via the BAL-RESEARCH-TELEBATRAC STUDY_RES secure messaging mail group link (see uploaded Interview Form in Section 5.0)

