 Novel_Robotic-Task_Bimanual_Assesment_Lowrey2014(0.01)	3/21/2017 10:03 AM	3/21/2017 10:03 AM
 References_MyHealtheVet SECURE MESSAGING PILOT STUDY(0.01)	10/3/2016 11:45 AM	10/3/2016 11:45 AM
 References from Grant Submission(0.01)	10/1/2015 1:39 PM	10/1/2015 1:39 PM
 Coupar et al. 2012_Home Based Therapy_Cochrane Review(0.01)	7/10/2014 11:53 AM	7/10/2014 11:53 AM
 Duncan et. al 2011_Body Weight Support TM_NEJM(0.01)	7/10/2014 11:52 AM	7/10/2014 11:52 AM
 Fearon et al. 2012_Early Supported Discharge_Cochrane Review(0.01)	7/10/2014 11:51 AM	7/10/2014 11:51 AM

ID: VIEW4E02805A7E400
Name: v2_Supporting Literature

Study Procedures

If you uploaded a separate research protocol document in the 'Research Protocol' page, cite the applicable section and page numbers from that document in the answer boxes below. (If this study is a collaborative UM/VA study please list each procedure that is being conducted and the locations where it is being conducted.)

1 * Describe all procedures being performed for research purposes only (these procedures would not be done if individuals were not in the study) and when they are performed, including procedures being performed to monitor subjects for safety or to minimize risks:

A) General Medical Evaluation: A general neurological evaluation will be conducted at baseline by a neurologist to confirm clinical diagnosis of stroke and review medical records relating to the index stroke. It also includes a review of questionnaires specific to depression and neurocognitive function (Center for Epidemiologic Studies Depression Scale [CESD] and Montreal Cognitive Assessment [MoCA]). Clinical suspicion or evidence on the CESD and MoCA of dementia, depression, severe aphasia,, or other major neuro-cognitive deficits that may interfere with the conduct of the study preclude further evaluation and initiate prompt referral to psychiatry or other specialist for evaluation.

B) Evaluations of Arm Function and Use: These will be performed at the VA by an evaluator blinded to treatment allocation and will occur three times at baseline, at final training (week 6-9), and after an 8 week no training retention period.

C) Questionnaires about arm use and participation will also be completed. The research evaluations are as follows below.

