1. eHealth Literacy Scale (eHeals): This is an 8-item questionnaire that measures your perceived ability and comfort using information technology for health. It will be used to gain an understanding of your electronic health literacy at the beginning and again at the end of the study. It should take approximately 5 minutes to complete.

2. Web-Based Learning Self-Efficacy Scale (WBLSES): This is an 8 to 12 item questionnaire used to rate your confidence using electronic tools for web-based online learning. Questions ask you to rate your opinion the MyHealtheVet instructions used, availability of assistance, amount of time available to complete the items, encouragement, physical conditions and computer navigation methods. It will be given at the outset of the study and again at the end of the study. It should take approximately 5 minutes to complete.

3. Montreal Cognitive Assessment (MoCA): The Montreal Cognitive Assessment is a 30-point screening instrument that has been validated to detect mild cognitive impairments or deficits in attention, memory, learning and visuospatial functions that may be due to neurological deficits consistent with stroke. The MoCA will be used to gain a general baseline of study participant's cognitive functioning and should take no more than 20 minutes to complete.

4. Interview: Post-training interviews will be completed after you receive instruction in using the MHV website for access to the secure messaging portal and mail group. This interview will be completed after your initial instruction and at any follow-up training. Questions will focus on your experience with the training and confidence using the site.

Qualitative Study Additional Procedures

1. Background Questionnaire: There are two versions of the background questionnaire; one designed for a study participant and one for staff and lab personnel employed by the VA Maryland Health Care System or University of Maryland. This is an 8-12 item questionnaire used to gather the study participants', staffs' or lab personnel's prior experience with the My HealtheVet patient portal and its tools prior to using it and or being involved in the design and implementation in the My HealtheVet Secure Messaging Pilot Study. It should take approximately 5 minutes to complete.

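### The pilot's eHEALS and WBLSES baseline is set after randomisation and is not tied to portal training, so it is taken with the arm known and could follow the training that Aim 3 evaluates

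*Combined protocol and SAP*

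**What the plan says.** The pilot baseline is described in Justification, Objective, & Research Design, item 2, under Intervention and Training. Those who opt into the pilot are seen for "baseline Standard Evaluations (eHeals, Web-based Self-Efficacy & MoCA, Post-training Interviews) following randomization and prior to initiation of the study intervention". The next sentence says that the home group is trained in secure messaging and interviewed straight afterwards.

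Earlier in item 2, participants and caregivers are offered the pilot at consent, but entry waits for allocation: they "will be enrolled in the pilot upon randomized to the Delayed Entry UC Group or the Home-based Telerehabilitation (HBT+TTT) group". Lab-arm participants are left out. The trial is called single blind, and the main repeated outcomes are assessed "by a study evaluator blinded to the intervention assignment".

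Aim 3 of the pilot is to "Determine efficacy of the two (2) one-hour structured MHV training on stroke survivors and caregivers Web-Based Learning Self-Efficacy Scores (WBLSES) and eHEALS scales". Its two hypotheses compare home-group scores at the end of the trial with baseline. Aim 4 Hypothesis 1 also uses an increase from baseline.

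Study Procedures, item 1, places eHEALS and the WBLSES at the start and end of the study, without saying how they fall relative to training. On the interview it says: "Post-training interviews will be completed after you receive instruction in using the MHV website".

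**The concern.** A baseline for judging training must come before the training. This one is fixed by two other events, randomisation and the start of the study intervention, and portal training falls between them. A post-training interview listed as part of the baseline set adds to the doubt about order.

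The second problem is that both scales ask for perceived ability or confidence. They are collected when the respondent already knows whether the next step is using the portal at home or a six-week wait, and that knowledge can move a self-rating in either direction.

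At stake are the Aim 3 and Aim 4 Hypothesis 1 changes from baseline, and any version of Aim 2 that adjusts for baseline. A late baseline could make useful training look ineffective, and the analysis could not recover the missing pre-training score.

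**Working it through.** The plan gives no figure to reproduce. The sample-size section concerns WMFT time only and states no sample size, SD, expected change or test for the pilot scales. The check is therefore on the order of events.

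**1. Is the arm known at baseline?** Yes. The scales follow randomisation, and entry to the pilot itself depends on the allocated arm. Only the evaluator is blinded, and the scales are completed by people who cannot be blind to home portal use versus waiting.

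**2. Where does portal training fall?** After allocation, because Study Procedures gives it only to those randomised to the home group. It would be expected before home exercise starts, because the functional tasks are delivered by secure message. Training and the pilot baseline therefore share one window.

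**3. Which orders satisfy the rule?** Both of these do:
- randomise → scales → training → home exercise
- randomise → training → scales → home exercise

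A baseline between training sessions also fits. Aim 3 speaks of two one-hour sessions, whereas Study Procedures gives about 15 minutes for portal training. These should be reconciled so that the training under test is defined.

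**4. What does each order do to the Aim 3 contrast?** Let *G* be the gain from the initial training, *L* any later change up to the end of the trial (including retraining and use), and *p* the share of *G* already achieved when the baseline is taken. Then

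end − baseline = (1 − *p*)·*G* + *L*

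- Scales first: *p* = 0, and the change is *G* + *L*.
- Between sessions: 0 < *p* < 1, and part of *G* is lost.
- All training first: *p* = 1, and only *L* remains.

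**5. What does knowing the arm do?** Let *e_H* and *e_D* be the shifts in the baseline rating in the home and delayed groups, of unknown size and sign. The home-group change becomes (1 − *p*)·*G* + *L* − *e_H*. The groups differ at baseline by *e_H* − *e_D*. A comparison of end scores alone contains neither term.

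**6. What does the alternative cost?** Each scale takes about 5 minutes, so 5 + 5 = 10 minutes. Equal allocation to three arms puts one third in the lab arm. As an upper bound, if all 78 randomised participants opted in, 78 / 3 = 26 would complete forms that the pilot does not use: 26 × 10 = 260 minutes in total, or 520 minutes if each also had a caregiver who opted in.

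**The case against.** The case for reading the plan as scales first is good. The Intervention and Training text mentions the baseline evaluations before the training. Study Procedures places the scales at the outset, and the delayed-entry paragraph speaks of pre and post evaluations. Portal training is described under the home-based intervention, so the study intervention could be taken to include it. The post-training interview is elsewhere defined as following training and, under Interviews, limited to the home group, so its place in the baseline list looks like loose drafting. A separate pilot protocol and a study flowsheet are listed as uploads and were not available here; they may fix the visit order.

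This makes scales first the likely intention, but none of it is a rule. Sentence order does not bind a site, outset is not defined relative to training, and the study intervention is not stated to include portal training. The WBLSES is also said to ask for opinions on the portal instructions used, which fits awkwardly with a respondent who has had none. Collection after randomisation is explicit on any reading.

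On Aim 2, the objection largely stands. Its hypotheses compare group scores and specify no change-score analysis, so a reader who infers that Aim 2 is biased as planned goes too far. Nor would an earlier baseline remove expectation effects from the end-of-study ratings, which stay unblinded.

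**Conclusion.** The point holds as a cheap improvement to an optional pilot. The plan requires a self-rated baseline taken with the arm known, and it permits, without stating, a baseline taken after portal training. In that order the Aim 3 and Aim 4 Hypothesis 1 changes would omit some or all of the initial training gain. Ratings made with the arm known may also differ between groups at baseline, which matters for the Aim 3 change and for any baseline-adjusted version of Aim 2.

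A reader might infer that the measured training effect is zero by construction. That needs all training to precede the scales and no later gain, and the documents say neither: training may span more than one session, and retraining is allowed. A reader might also multiply an assumed shift per item across the eight eHEALS items to put points on the expectation effect. The documents give no basis for such a shift, so the size is left unquantified.

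The conclusion rests on the wording of this document alone and on participants learning their arm before the pilot baseline. The WMFT primary outcome is untouched, because main-study baseline testing is completed before randomisation.

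**What to change.** Amend the pilot paragraph under Intervention and Training so that participants and caregivers who opt into the pilot at consent complete eHEALS and the WBLSES in the baseline phase, before randomisation and before any MHV training. Take the post-training interview out of the baseline list and give it separately as an after-training item for the home group. Leave the MoCA as it is: the one done at the medical evaluation belongs to the stroke participant and does not cover caregivers.

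The enrolment sentence in item 2 needs a small change so that these two forms can precede entry to the pilot. The running cost is about 10 minutes per person at an existing visit, spent without use on the roughly one third later allocated to the lab arm and their caregivers. If collection before randomisation is not acceptable, stating that both scales precede any portal training would settle the order for Aim 3, but the ratings would still be made with the arm known.
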